14. DATA HANDLING AND RECORDKEEPING

14.1 Data Management Responsibilities

This study will be conducted a 16 field sites throughout India, but will be coordinated by a single site, the YR Gaitonde Centre for AIDS Research and Education (YRG CARE) in Chennai, Tamil Nadu, India with oversight from investigators at the Johns Hopkins Bloomberg School of Public Health and the Johns Hopkins School of Medicine. Investigators from Johns Hopkins and YRG CARE will oversee all aspects of the trial including participant recruitment, data collection, laboratory testing, biological sample storage, and data management. Additional details can be found in the Data and Safety Monitoring Plan.

14.2 Essential/Source Documents and Access to Source Data/Documents

Source documents for this study are i) electronic case report forms (eCRFs), into which data from interviews will be directly entered, and ii) government ART treatment books, which will be photocopied and stored electronically at each study visit. Additional details can be found in the Data Safety and Monitoring Plan.

14.3 Quality Control and Quality Assurance

14.3.1 Procedures to ensure the validity and integrity of the data

All field staff, interviewers, phlebotomists and clinicians who will come into contact with study participants will be required to complete research ethics and good clinical practice (GCP) training.

Lab technicians/phlebotomists at YRG CARE have undergone training on research ethics and good clinical laboratory practices (GCLP). The YRG CARE ID Lab is certified by the College of American Pathologists, United Kingdom National External Quality Assurance Scheme, and the Virologic Quality Assessment Program, US and by the AIDS Clinical Trials Group and Abbott Laboratories Inc, US to perform HIV-1 genotypic resistance testing. GCLP are monitored by Johns Hopkins, Family Health International, and PPD.

14.3.2 Procedures to guarantee the accuracy and completeness of the data

Our primary mode of data collection will be through the EHR at the ICCs and study specific eCRFs. Additional details can be found in the Data Safety and Monitoring Plan.

15. CLINICAL SITE MONITORING

ICCs are key population-focused sites that provide HIV and HCV testing, STI screening and treatment, and (in PWID sites) OST and SSP. They are staffed by a site coordinator, one or two nurses, a counselor, a phlebotomist, and a part-time physician. This ICC staff provided clinical overview for the site. The current study evaluates a behavioral economic intervention, which is minimal risk. No additional clinical monitoring is needed for the current protocol.

16. HUMAN SUBJECTS PROTECTIONS

16.1 Institutional Review Boards

The protocol and informed consent documents are approved by the Institutional Review Boards of the Johns Hopkins School of Medicine in the US and YRG CARE in Chennai, India. In addition, the study is approved by the Indian Council of Medical Research and the Health Ministry Screening Committee. Any subsequent modifications will be reviewed and approved by both the Johns Hopkins and the YRG CARE IRBs. IRB continuing review and approval will be obtained from both the Johns Hopkins and YRG CARE IRBs once a year. If IRB approval expires or lapses, all ongoing research activities will stop unless the PIs determine that it is the best interests of already enrolled participants to continue their study-related activities. New participants will not be enrolled in the study until the IRB approval to continue the research is obtained.

16.2 Vulnerable Participants

16.2.1 Pregnant Women and Fetuses

Pregnant women who meet eligibility criteria for inclusion in the PWID stratum of the study may be included in any aspect of the study (cohort, mixed methods evaluation, or RDS survey). The study does not provide medications or interventions that pose a risk to pregnant women or their fetuses. We will not test women for pregnancy as part of this study.

16.2.2 Prisoners

It is possible that persons who are enrolled may become prisoners during the course of the study. We do not have formal agreements in place to provide the incentive intervention or conduct study visits while participants are in prison. We will not conduct any research activities while participants are in prison. We will continue to track participants and re-engage them in the study when they are released from incarceration if still in the follow-up window.

16.2.3 Children

Children younger than 18 years will not be included in any aspect of the study.

16.2.4 Illiterate participants

Some of our research participants will be illiterate. As required by the JHM and YRG CARE IRB, all informed consent documents will be read verbatim.

16.3 Informed Consent

16.3.1 Informed Consent Process

Study cohorts: Written informed consent will be used for HIV-positive participants enrolled in the cohorts at each ICC. Consent will be obtained by a trained, supervised research assistants in a private office setting. Approximately 20 minutes will be allotted for consent. Participants will not generally have access to the consent form in advance, but they may take a consent form with them if they wish to take more time in making a decision to join the study. The research assistants will present the consent form to participants in detail and encourage them to ask questions. The research assistants will assess participation understanding of the consent form by querying whether 1) identifying information will be collected in the study (yes), and 2) whether the study will have any follow-up after the initial visit (yes, we will use locator information to locate participants at the end of the study and ask them questions about their HIV care and get a sample of blood). Because this study will be conducted in numerous cities across India, multiple translations are needed to accommodate local languages.

In-depth interviews: A research assistant will meet with individuals in a private office to describe the study and obtain oral consent. The research assistant will read the OCS verbatim to potential participants in the relevant language for the study site.

RDS survey: We will use an oral consent script for RDS participants. With the exception of the

RDS “seeds” (2 or 3 participants to begin the recruitment chain), individuals must present a valid to the study site with a valid referral coupon. A research assistant will meet with such individuals in a private office to describe the study and obtain oral consent. The research assistant will read the oral consent script verbatim to potential participants in the relevant language for the study site.

16.3.2 Assent Process

Not applicable

16.3.3 Documentation of Informed Consent

Participants who provide written consent will be given a copy of the consent. In addition, a signed copy of the consent will be maintained in locked cabinets at each of the study field sites.

16.4 Risks

a. Medical risks, listing all procedures, their major and minor risks and expected frequency.

Study procedure	Medical Risks	Frequency	Severity
HIV-positive ICC cohort participant	Pain from phlebotomy	Most	Minor
	Phlebitis or skin infection from phlebotomy	< 1%	Minor to moderate
In-depth interviews	None		
Baseline/Evaluation RDS	Pain from phlebotomy	Most	Minor
	Phlebitis or skin infection from phlebotomy	< 1%	Minor to moderate
	Psychological discomfort from questions about personal behaviors	< 20%	Minor
	Anxiety about HIV testing	Most	Minor

b. Steps taken to minimize the risks.

The proposed study poses only minimal medical risks. We will minimize the risk of phlebotomy-associated adverse events by using trained and experienced phlebotomists and by adhering to sterile practice. We will minimize the risk of participant discomfort with personal questions by a) training interviewers to query and respond in non-judgmental manner and b) to inform participants that they may skip questions they are not comfortable answering. Finally, we will minimize anxiety about HIV testing by using trained HIV testing counselors.

c. Plan for reporting unanticipated problems or study deviations.

The Indian co-investigator ([name]) will report unanticipated problems and study deviations to the local IRB (YRG CARE IRB). Such events will also be communicated with the US investigators and [name] (JHU PI) will report to the JHM IRB. [name] will report unanticipated problems or study deviations that involve risks to participants or others

promptly to the JHM IRB in accordance with Organization Policy. Minor problems and protocol deviations (which pose no risk to subjects or others) will be reported in annual protocol continuing review.

d. Legal risks such as the risks that would be associated with breach of confidentiality.
We will collect self-reported information on illicit drug use and sexual practices that may pose legal risks to participants if confidentiality is breached. Regarding the HIV-positive ICC cohort participants, we will collect identifying information in these subjects, including name, address, and contacts. These data will be maintained at the sites on password-protected laptops that will be brought home by study staff each night. As with the RDS, data will be uploaded each night to an encrypted, internet-based clinical trial database, based at YRGACRE in Chennai. Source documents on-site will be maintained in a double-locked file cabinet.

Regarding the RDS surveys, we have a multilevel plan to minimize this risk. First, we will not collect RDS participants' names or other identifying information, and we will use oral consent to avoid the use of names and signatures on informed consent forms. Second, RDS interview data will be uploaded immediately to an encrypted, internet-based clinical trial database. RDS interviewers in the field will not have access to participant data in the database other than the participant they are currently interviewing. Third, interview and laboratory data will be stored and managed at the YRGACRE coordinating center in Chennai, India. These data will be password-protected and available only to a defined group of data managers and analysts who are working on the trial.

e. Financial risks to the participants.
This study entails no financial risks to participants.

16.5 Social Impact Events

Individuals enrolled in this study may experience personal problems resulting from the study participation. Such problems are termed social impact events. Although study sites will make every effort to protect participant privacy and confidentiality, it is possible that participants' involvement in the study could become known to others, and that participants may experience stigmatization or discrimination as a result of being perceived as being HIV-infected. For example, participants could be treated unfairly, or could have problems being accepted by their families and/or communities. Problems may also occur in circumstances in which study participation is not disclosed, such as impact on employment related to time taken for study visits.

In the event that a participant reports a social impact event, every effort will be made by study staff to provide appropriate assistance, and/or referrals to appropriate resources. Social impact events are documented and reviewed on a scheduled basis by the protocol team leadership with the goal of reducing their incidence and enhancing the ability of study staff to mitigate them when possible. Social impact events that are judged by the designee to be serious, unexpected, or more severe or frequent than anticipated, will be reported to the overseeing IRBs in accordance with the IRB's reporting policy.

16.6 Benefits

Participants in the HIV-positive ICC cohorts, have the potential to benefit if the intervention leads to improved HIV treatment outcomes and retention to care. Persons who participate in the RDS may benefit from HIV counseling and testing and learning their HIV status. No benefits are anticipated for those who participate in in-depth interviews. The study has the potential to benefit society if the tested intervention is found effective and are adopted in routine service delivery.

16.7 Compensation

HIV-positive cohort participants will receive 250 Indian Rupees (4.17 USD) for successfully completing each study visit (maximum of 5 visits). For the last 2 visits (18-month and 24-month visits) we will offer a bonus of 200 Indian Rupees (3.33 USD), in addition to the base reimbursement, for participants who complete the visits in a +/- 14 day window around the scheduled visit date. The maximum possible reimbursement for ICC cohort participants is 1650 Indian Rupees (27.50 USD) for those who complete all 5 study visits and complete the last 2 visits within the specified window.

Compensation for time and travel will be provided to in-depth interview participants – 150 Indian Rupees (2.50 USD).

Compensation will be provided to RDS participants. They will receive 250 Indian Rupees (4.17 USD) for completing the survey and phlebotomy. They will also be eligible to receive an additional payment for each coupon returned by an eligible participant up to 2 coupons maximum (50 Indian Rupees or 0.83 USD per coupon). Thus, the maximum possible compensation for RDS participants will be 350 Indian rupees (6.83 USD).

16.8 Participant Privacy and Confidentiality

All participant-related information including eCRFs, laboratory specimens, evaluation forms, reports, etc., will be kept strictly confidential. All paper records will be kept in a secure, double-locked location and only research staff will have access to the records. For electronic records, an encrypted network-based data collection storage system will be used. Trained interviewers will conduct face-to-face interviews with participants and enter responses directly onto a laptop computer or tablet. Information will be routed directly to a central server via a local network. Encrypted data will then be transferred over the internet (a minimum of once daily) to the central data storage at YRG CARE where it is stored and backed-up every 24 hours. Data will be cleaned at YRG CARE and de-identified before being encrypted and transferred via a secure internet portal to the analytical team at Johns Hopkins. Human specimens (blood) will be labeled using study specific ID numbers only, with no personal identifying information on the tube or paperwork. Samples will be shipped under specified conditions and time frames to YRG CARE for laboratory testing. The biometric system that will be used generates a unique and reproducible hexadecimal code when a fingerprint is scanned or rescanned. The software does not store fingerprint images and hexadecimal codes cannot be back-converted to a fingerprint image.

Only the field teams delivering care to participants will have access to identifying information of

study participants. Any data that is sent to US investigators for analysis will be deidentified. Upon request, participant records will be made available to the study sponsor, the sponsor's monitoring representative and applicable regulatory entities.

16.9 Certificates of Confidentiality

This study is protected by a Certificate of Confidentiality for data stored in the U.S. Certificates of confidentiality are not recognized by the Indian Government.

16.10 Study Discontinuation

The study may be discontinued at any time by the IRB or NIDA as part of their duties to ensure that research participants are protected.

16.11 Post-Trial Access

Not relevant

16.12 Community Advisory Board and Other Relevant Stakeholders

Community advisory boards are already present in each of the study field sites as part of ongoing research activities and they will continue to be engaged throughout this protocol. Community meetings will occur quarterly.

17. ADMINISTRATIVE PROCEDURES

17.1 Protocol Registration

Not applicable

17.2 Regulatory Oversight

Not applicable

17.3 Study Implementation

Additional details can be found in the Study standard operating procedures (SOP)

17.4 ClinicalTrials.gov

This trial is registered with ClinicalTrials.gov – NCT02969915

19. APPENDICES

Appendix I. Schedule of procedures and evaluations for cohort participants followed in cluster randomized trial

Procedures/Evaluations	Screening	Baseline visit	Follow-up evaluations and intervention				
			6 mo.	12 mo	18 mo	24 mo	Interim visits
Screening questionnaire	X						
Enrollment informed consent	X						
Register biometric code (fingerprint based) in database		X					
Abstract HIV treatment data from govt. ART books	X		X	X	X	X	X
Locator information		X	X	X	X	X	X
Study interview							
Demographics		X					
Quality of life		X	X	X	X	X	
HIV care continuum		X	X	X	X	X	
ART use & adherence		X	X	X	X	X	
Beliefs about ART		X	X	X	X	X	
Drug & alcohol use		X	X	X	X	X	
Drug related risk behaviors		X	X	X	X	X	
Sexual risk behaviors		X	X	X	X	X	
Depressive symptoms		X	X	X	X	X	
Healthcare utilization		X	X	X	X	X	
Laboratory tests							
Rapid HIV test	X						
CD4 cell count		X					
HIV RNA		X	X	X	X	X	
Blood glucose			X				
Creatinine				X			
Hepatic panel					X		
Study visit compensation		X	X	X	X	X	
HIV care incentives provided (intervention sites only)			X	X	X	X	X

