10.2 Laboratory Evaluations

Laboratory evaluations for the study cohort in the cluster randomized trial

- HIV RNA will be measured from plasma at all cohort study visits by the central laboratory (YR Gaitonde Centre for AIDS Research and Education [YRG CARE]) in

Chennai, India using RealTime HIV-1 (Abbott Laboratories, Abbott Park, IL, USA). The HIV RNA result at the 24-month visit will be shared with participants

- CD4 cell counts will be measured at baseline by flow cytometry in a local or regional laboratory. The CD4 test result will be shared with participants.
- At the 6-month, 12-month, and 18-month cohort visits we will measure serum glucose, serum creatinine, and a liver function panel, respectively. These assays will be conducted at local or regional laboratories. Results from these tests will be shared with participants as a value-added benefit of participating in the trial.

Laboratory evaluations for mixed methods evaluation of incentives

None

Laboratory evaluations for RDS survey

- Rapid HIV testing - This point-of-care testing will be used to test all RDS participants. The rapid testing protocol includes the use of 3 rapid test kits in an algorithm: Alere Determine HIV-1/2 (Alere Medical, Chiba, Japan), First Response HIV Card test 1-2.0 (Premier Medical Corporation, Daman, India), and Signal Flow Through HIV 1+2/Immunodot Test Kit (Span Diagnostics, Surat, India).
- HIV-1 RNA - HIV RNA will be measured from plasma in HIV-positive survey participants by the central laboratory (YRG CARE) in Chennai, India, using RealTime HIV-1 (Abbott Laboratories, Abbott Park, IL, USA).
- CD4 cell count - CD4 cell counts will be measured in all HIV-positive participants by the central laboratory (YRG CARE) in Chennai, India using Flow Cytometry (EPICs XL-MCL, Beckman Coulter, Inc., USA).
- Recent HIV infection - Recent HIV infection will be assessed using a validated multi-assay algorithm in all HIV-positive survey participants. The algorithm testing includes Limited Antigen (LAG) Avidity EIA (Maxim Biomedical Inc, Rockville, MD, USA) and the JHU-modified Bio-Rad Avidity assay (Bio Rad Laboratories, Hercules, CA, USA). Individuals are characterized as having recent infection if CD4 count >50 cells/mm³, HIV RNA >400 copies/mL, LAG avidity <2.9 OD-n, and JHU-modified Bio-Rad avidity index <85% (5).

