13.2.2 Secondary Endpoints

- Survival with suppressed viral load at 6, 18, and 24 months.
- Proportion with at least one suppressed viral load during study follow-up (6, 12, 18, or 24 months).
- Time to ART initiation, recorded from government HIV treatment records, among cohort participants that were ART-naïve at baseline.
- Retention to HIV care during follow-up, defined as having 1 or more visits to a government ART clinic in each 6-month period of study follow-up.
- ART possession ratio (a measure of medication adherence), defined as the time in possession of ART divided by the follow-up time. Follow-up time will commence at enrollment for ART-experienced participants and at ART initiation for ART-naïve participants. Follow-up time will be censored at the end of trial follow-up, death, or loss-to-follow-up. The amount of time in possession of ART will be determined from ART dispensation logs maintained by government HIV clinics.
- Mortality, defined as a report of a participant's death from a family member or a close

friend. Death records are not maintained by local, state, or national governments in India.

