13.9.1 Analysis plan for primary outcome

In the primary analysis, we will use an intent-to-treat, missing equals failure approach. The primary outcome will be the proportion of participants who have survived with a suppressed viral load (HIV RNA <150 c/mL) at the 12-month cohort follow-up visit. Participants that die prior to the 12-month visit or miss the 12-month visit will be considered failures in the analysis. The primary analysis will be at the site-level and will use a two-stage procedure beginning with fitting an individual-level logistic regression model with terms for each matched pair and individual-level viral suppression at the baseline visit (HIV RNA <150 copies/mL), but ignoring the intervention effect. The model computes the expected number of events in each cluster. The observed and expected number of events in the two clusters in each matched pair are compared and if there is no intervention effect these values will be the same. An adjusted prevalence ratio and 95% confidence interval will be calculated by estimating the mean within-pair difference of the natural log transformed adjusted prevalences by arm. The exponentiated difference is the ratio and a paired t-test will be used for significance testing. An adjusted prevalence difference and 95% confidence interval will be calculated in a similar manner, estimating the mean within pair difference of the non-transformed prevalences by arm. Analysis of the primary outcome will also be stratified by viral suppression status at baseline (HIV RNA <150 copies/mL). In this site-level one-stage approach, we will calculate the difference in the proportion with suppressed viral load within each matched pair among strata defined by baseline viral suppression. We will calculate the unweighted mean of the pair-wise difference with a 95% confidence interval and use a paired t-test to test the hypothesis that within each stratum the observed difference is statistically different from zero. We will further explore whether there is statistically significant interaction by baseline viral suppression status and intervention effect.

Primary outcome sensitivity analyses

We will conduct several supplemental analyses to assess whether inferences are sensitive to different analytic specifications. First, we will conduct an analysis in which participants who

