miss the 12-month visit (but are not known to be deceased) will be excluded (missing ignored), and death or non-suppression of the HIV RNA at month 12 will be considered failure. Second, we will conduct an analysis that includes only individuals that complete the 12-month visit (deaths and missing ignored) and non-suppression of the HIV RNA at month 12 will be considered failure. In a third sensitivity analysis, we will consider adjusting for additional potential confounders using the same two-stage procedure described above (6). We will only consider factors measured at the baseline visit (no post-randomization measures) that have a large (odds ratio >2 or <0.5) and statistically significant ($p<0.05$) association with the intervention status and the outcome. Fourth, we will conduct pre-specified analyses that are stratified by key population (PWID and MSM).

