13.9.2 Secondary outcomes

Secondary binary outcomes including i) survival with suppressed viral load at other time points (6, 18, and 24 months), ii) proportion with at least one suppressed viral load during follow-up, iii) proportion retained to HIV care (defined as the proportion with at least one visit to the ART center per 6-month follow-up interval), and iv) mortality will be analyzed similarly resulting in pair-wise differences in proportions with a two-stage procedure for confounder adjustment, if appropriate (criteria for confounders outlined in prior section).

For two other secondary outcomes, we will use similar pair-matched cluster approaches with a two-stage procedure for confounder adjustment. First, we will compare risk of initiating ART at intervention vs. control sites (among the subset that is ART-naïve at baseline) using a Cox proportional hazards model. Second, we will compare ART possession ratio (defined as number of days covered by ART dispensations divided by the number of days under observation) by calculating a mean difference between intervention and control conditions.

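### Baseline CD4 can enter the mortality comparison only through a confounder rule it would rarely satisfy, so a collected and probably prognostic covariate will almost always be left out

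*Combined protocol and SAP*

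**What the plan says.** Section 10.2 states that "CD4 cell counts will be measured at baseline by flow cytometry in a local or regional laboratory". Appendix I lists "CD4 cell count" at the baseline visit and at no other. By section 13.6, the allocation of each pair was withheld until recruitment at both sites was complete or nearly so, so almost all of these values precede any knowledge of arm.

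The first-stage model for the primary outcome (13.9.1) has "terms for each matched pair and individual-level viral suppression at the baseline visit" and no arm term. CD4 is not in it. The third sensitivity analysis in the same section opens the model to other covariates: "We will only consider factors measured at the baseline visit (no post-randomization measures) that have a large (odds ratio >2 or <0.5", with p below 0.05, on the "association with the intervention status and the outcome".

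Section 13.9.2 then says that "mortality will be analyzed similarly resulting in pair-wise differences in proportions with a two-stage procedure for confounder adjustment, if appropriate", and refers back to those criteria. Mortality is a secondary objective in its own right (6.2).

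Site matching (13.5) and the restricted randomization (13.6) do not use CD4. The one analytic use of CD4 that is spelled out is the recent-infection algorithm for the RDS survey (10.2), which is not a cohort analysis. The documents give no expected mortality, no CD4 distribution and no estimate of how CD4 relates to death.

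**The concern.** A covariate measured before the intervention is worth adjusting for when it predicts the outcome, whether or not it happens to differ between arms. The rule in 13.9.1 instead makes entry depend on a large and significant difference between arms as well. In a randomized comparison that difference arises only by chance, so the rule selects on the size of an accident.

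The effect falls on mortality. The comparison rests on 8 pair differences. If the two cities of a pair differ in their share of participants with low CD4, and low CD4 raises the risk of death, the difference passes into the mortality contrast. Adjustment in the individual-level first stage could remove part of it without using any of the degrees of freedom of the paired t-test. Under the rule as written, that adjustment would seldom be made.

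**Working it through.** **The plan's own figure.** Nothing is stated for mortality or CD4. The only power statement (13.4) concerns the primary endpoint. I read its formula with the squared difference as divisor, n = 150 per cluster and two-sided 0.05. For 25% vs 33% at k_m 0.10:

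c = 2 + (1.960 + 0.842)² × [0.25×0.75/150 + 0.33×0.67/150 + 0.10²×(0.25² + 0.33²)] / 0.08² = 7.44.

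For 25% vs 35% at k_m 0.15, c = 7.44; for 40% vs 50% at k_m 0.10, c = 7.78. All three round up to 8 pairs, as stated. The 8 pairs and 150 per site carry into the checks below.

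**How large an imbalance the rule requires.** Assume 30% with low CD4 in one arm. The odds are 0.30/0.70 = 0.429. Doubled they are 0.857, which is 0.857/1.857 = 46% in the other arm. That is a gap of 16 percentage points between two arms of 8 × 150 = 1,200 people each.

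**How often it would occur.** The first simulation had no intervention effect, 8 pairs, 150 per site and 400 runs per setting. Assumed inputs, none from the documents:
- mortality 5, 10 or 15%;
- 30% with low CD4;
- odds ratio for death with low CD4 of 2, 3 or 5;
- residual site SD 0.15 on the logit scale;
- between-site SD of the logit low-CD4 share of 0, 0.3 or 0.6, drawn independently for the two sites of a pair.

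The first stage had pair terms and low CD4. The adjusted pair difference is the difference between sites in mean (observed − expected). Variance reduction is 1 − Var(adjusted)/Var(unadjusted).

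| SD of site CD4 mix (logit) | 95% range of arm-CD4 odds ratio | Odds ratio beyond 2 or 0.5 | Variance reduction |
|---|---|---|---|
| 0 | about 0.8-1.2 | 0% | 1-7% |
| 0.3 | about 0.7-1.4 | 0% | 2-20% |
| 0.6 | 0.53-1.82 | 0.3-3% | 10-50% |

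Only the size of the arm association was counted. The significance condition and the condition on the outcome can only lower these frequencies.

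**One setting in numbers** (mortality 10%, odds ratio 3, SD 0.3). The standard error falls from 0.0155 to 0.0147, and 1 − (0.0147/0.0155)² = 10%.

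The model is logit(p) = logit(0.10) + ln 3 × (low − 0.3). It gives mortality of 7.4% without low CD4 and 19.3% with it, a gap of 11.9 points. The upper end of the arm-CD4 odds ratio in this setting was 1.38. From 30%, the odds become 0.429 × 1.38 = 0.591, or 37.2%, a gap of 7.2 points. This moves the mortality difference by 0.072 × 0.119 = 0.0086, about 0.9 percentage points. That is a little over half the unadjusted standard error, and the rule would still exclude CD4.

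**A second set of assumptions.** Mortality 14% at PWID sites and 6% at MSM sites, 25% with low CD4, residual site CV 0.15, true mortality ratio 0.65. Two separately written simulations, each with 1,500 runs per setting, compared CD4 adjustment with crude differences:

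| Odds ratio; SD of site mix | Variance reduction | Power, crude to adjusted | Size part of arm condition met |
|---|---|---|---|
| 2; 5 points | 2-3% | 0.59-0.60 to 0.60-0.62 | 0% |
| 3; 8 points | 9-10% | 0.55 to 0.59-0.60 | 0.1-0.6% |
| 5; 8 points | 18-24% | 0.51-0.53 to 0.62-0.63 | 0.3-0.4% |
| 5; 12 points | 35-38% | 0.42 to 0.57-0.58 | 3.8-4.3% |

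Type I error with adjustment stayed at or below about 5%. The frequencies in the last column come from one of the two simulations, run with and without an effect.

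**The case against.** The strongest reply is that the plan already provides for this. CD4 is measured at the baseline visit, so 13.9.1 and 13.9.2 make it an eligible covariate for mortality. That is correct. A reader might infer that mortality can only be compared crudely, or that the cohort analyses shut CD4 out; the documents do not support either reading. What survives is that the entry rule would seldom be met.

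A reader might also infer that the pairs are imbalanced on CD4. That does not follow. Not matched is not the same as not balanced, and no document reports CD4 by site. Pairs share key population and former ICC status, geography was considered, and site-level suppression and viremia were used in both matching and restriction. Nor is the unadjusted comparison invalid: randomization protects it, and its confidence interval reflects chance imbalance.

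Three further objections limit the gain:

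- **Laboratories.** Cohort CD4 is run locally or regionally, so laboratory differences may coincide with site. A simulation with 1,000 runs used the second set of mortality assumptions, an odds ratio of 3 and an assumed site-level shift in CD4 classification. With a shift SD of 0.3 of a CD4 SD, adjustment changed the variance by −4% (site-mix SD 8 points) or +6% (5 points). At 0.5 the changes were about 0% and +10%, and power fell from 0.53 to 0.51 and from 0.61 to 0.56. The size of the shift is assumed, but forced adjustment could lose precision.
- **Death rate.** At an assumed 6% and 2% mortality, the gain at odds ratios of 2 to 3 is 1-4%, and power moves by about 0.02 or less.
- **Comparator.** All gains are against crude differences. If the baseline suppression term carries over to mortality, the gain from CD4 beyond it has not been shown.

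All three stand. They reduce the expected benefit; they do not defend an entry rule based on chance imbalance.

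**Conclusion.** The point holds as a minor improvement to one secondary endpoint. CD4 is collected before the intervention, no cohort analysis names it, and the rule by which it could enter the mortality model was met on size in about 0-4% of simulated trials. The plan as written would therefore nearly always omit it, even when it is prognostic and moderately imbalanced.

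The size of the loss cannot be fixed from the documents. It depends on assumed mortality, CD4 distribution, CD4 effect and variation in site mix. A fair statement is 1-7% of variance with a similar CD4 mix at paired sites and roughly 2-20% with moderate differences. More is gained only with strong CD4 effects and large site differences, and laboratory variation could cancel it. A reader might infer that the trial's main result is at risk. It is not: neither the primary endpoint nor its analysis is touched.

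**What to change.** In 13.9.2, fix the first-stage model for mortality before deaths are examined by arm:

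- Include matched-pair terms and baseline CD4, regardless of its association with arm. Use broad categories with cut-points set in advance, or log CD4, and add a missing category.
- State whether the baseline viral suppression term from the primary model also applies to mortality. The present wording leaves this open.
- Report the unadjusted pair-wise difference alongside the adjusted one, so that any effect of laboratory variation on the adjusted result can be seen.

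The cost is a sentence or two of analysis plan. The data are already collected, and the paired t-test on 8 differences keeps its degrees of freedom. The one risk is the loss of precision if local CD4 measurements differ systematically between sites; broad categories and the unadjusted result are there to limit and reveal that.
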